#### **9.4.1.2 Pharmacokinetics Endpoints**

Pharmacokinetics endpoints are exploratory endpoints in this study:

- Pharmacokinetic parameters (eg, Ctrough, Cmax, tmax, t1/2, AUC0-12) (Part 1)
- Pharmacokinetic concentrations (eg, C8hr) (Part 2)

#### **9.4.2 Safety Endpoints**

A description of safety measures is contained in Sections 8.3 and 8.4. The analysis of safety results is described in Section 9.6.2.

The safety analysis endpoints include:

- The proportion of: 1) participants with at least 1 AE; 2) participants with at least 1 drug-related AE; 3) participants with at least 1 SAE; 4) participants with at least 1 serious and drug-related AE; 5) participants who discontinued study intervention due to AE; 6) participants who discontinued study intervention due to a drug-related AE; and 7) participants with AE(s) leading to death. The AE reporting period is from the time of randomization through 14 days following cessation of treatment. Additional reporting periods will be used as appropriate (eg, throughout the study for SAE).
- Events of Clinical Interest specified in Section 8.4.7.

#### **Predefined Limits of Change (PDLC) in Laboratory Parameters**

For the summaries of laboratory tests, participants must have both a baseline and post-randomization on-treatment measurement to be included. Participants' laboratory values (based on their most abnormal laboratory test values, in the direction of interest, while on study intervention) will be classified as to whether or not they fall outside of the PDLC and are worse in grade (i.e., more abnormal in the direction of interest) than at baseline. The criteria will be adapted from the DAIDS table for Grading the Severity of Adult and Pediatric Adverse Events, July 2017, version 2.1. A listing of the participants who meet the criteria will also be provided.

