NP and OP Swabs		X		X		X	X	X	X		Based on Part 1 data, NP and OP swab collection may be adapted to remove one method or timepoints throughout the life of the study; this will be communicated via Protocol Clarification Letters.
Serum and Plasma for Exploratory Research		X				X	X		X		Research samples will be stored for testing as described in Sections 4.2.5 and 8.8.
Serum for Antibody Exploratory Research		X				X	X		X		

Study Period:	Screening	Intervention					Follow-Up				Notes
Visit Number/Title:	1	2	3	4	5	6	7	8	9	10	
Scheduled Day (and Window):	Screening ( $\leq 24$ hours before rand.) a	Day 1 b	Day 2	Day 3	Day 4	EOT	Day 10 ( $\pm 1$ day)	Day 15 (+3 days)	Day 29 (+3 days)	LFU Month 7 ( $\pm 1$ Month) c	
Assessment of COVID-19 Signs, Symptoms, Functional Status		X	X	X	X	X	X	X	X		Assess signs and symptoms daily while hospitalized and only at study visits after discharge. Functional status only assessed at Day 1, Day 3, EOT, Days 10, 15, and 29. Assessment will not be done at virtual visits.
Assessment of Level of Consciousness (AVPU)		X				X					
Respiratory/ Oxygenation Status		X	X	X	X	X	X	X	X	X e	SpO 2 measured daily while hospitalized via pulse oximetry. If applicable: FiO 2 , PaO 2 , and supplemental oxygen use. SpO 2 will not be done at virtual visits.
Hospitalization Status		X	X	X	X	X	X	X	X	X	Discharge readiness will be assessed daily while hospitalized.
Survival Status									X	X	
Safety Procedures											
Full Physical Examination	X										Including height and weight
Directed Physical Exam		X		X		X	X	X	X		
Vital Signs	X	X	X	X	X	X	X	X	X		Heart rate, blood pressure, respiratory rate, temperature. Assess vitals daily while hospitalized and only on study visits after discharge.

Study Period:	Screening	Intervention					Follow-Up				Notes
		2	3	4	5	6	7	8	9	10	
Scheduled Day (and Window):	Screening ( $\leq 24$ hours before rand.) a	Day 1 b	Day 2	Day 3	Day 4	EOT	Day 10 ( $\pm 1$ day)	Day 15 (+3 days)	Day 29 (+3 days)	LFU Month 7 ( $\pm 1$ Month) c	
Blood Collection for Local Laboratory Evaluation	X d										Local laboratory collection required unless chemistry/hematology results within 72h prior to randomization are available.
Blood Collection for Central Laboratory Evaluation		X		X		X	X	X	X		Hematology and Chemistry at all indicated time points. Inflammatory biomarkers at Day 1 and EOT only.

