12-lead ECG	X	X									If ECG is conducted at Screening, then do not repeat on Day 1.
Serum Pregnancy Test (hCG; WOCBP only)	X d							X			
Confirm Contraception Requirements (WOCBP and male participants)		X		X		X	X	X	X	X	Confirm participant compliance with contraception requirements as outlined in inclusion criteria and Appendix 5
Urinalysis		X									
AE/SAE Review h	X	X	X	X	X	X	X	X	X		
Pharmacokinetics											
PK Plasma Sampling						X					Part 1: 

Pre-dose, 1, 3, 5, 8 hours post-dose

 Part 2: 

Pre-dose, 1, 5 hours post-dose

Study Period:	Screening	Intervention					Follow-Up				Notes
		2	3	4	5	6	7	8	9	10	
Scheduled Day (and Window):	Visit Number/Title: Screening ( $\leq 24$ hours before rand.) a	Day 1 b	Day 2	Day 3	Day 4	EOT	Day 10 ( $\pm 1$ day)	Day 15 (+3 days)	Day 29 (+3 days)	LFU Month 7 ( $\pm 1$ Month) c	
PK PBMC Sampling i						X					Part 1 (PBMC Cohort only): 
 
Pre-dose, 1, 3, 5, 8 hours post-dose
 

AE=adverse event; ALT=alanine aminotransferase; AST=aspartate aminotransferase; AVPU=Alert, Voice, Pain, Unresponsive; COVID-19=coronavirus disease 2019; ECG=electrocardiogram; EOT=End of Treatment (day of last study intervention dose); FiO2=fraction of inspired oxygen; hCG=human chorionic gonadotropin; HBV=hepatitis B virus; HCV=hepatitis C virus; HIV=human immunodeficiency virus; LFU= Late Follow-Up; IRT=intervention randomization system; NP=nasopharyngeal; OP=oropharyngeal; PaO2=partial pressure of oxygen; PBMC=peripheral blood mononuclear cells; PSV= Pregnancy Status Visit; PK=pharmacokinetic; rand.=randomization; RNA=ribonucleic acid; SARS-CoV-2=severe acute respiratory syndrome coronavirus 2; SAE=serious adverse event; SpO2 = oxygen saturation; WOCBP=women of childbearing potential.

a Screening and Day 1 (randomization) can be done in same session. Study assessments should not be duplicated if screening and Day 1 (randomization) are completed on the same day.

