### **4.3 Justification for Dose**

#### **4.3.1 Rationale for Dosing Duration**

Three doses of MK-4482 (administered every 12 hours) were sufficient to demonstrate efficacy in a ferret model of influenza. However, the duration of dosing of MK-4482 required to achieve efficacy against SARS-CoV-2 in humans is unknown. The planned treatment regimen of 5 days in this study is consistent with other acute antiviral treatments such as oseltamivir for influenza and is supported by nonclinical and clinical safety data for MK-4482.

In a 28-day toxicity study of MK-4482 at 17 mg/kg/day (2.2-fold the predicted NHC exposure of 13.27  $\mu$ M\*hr at a dose of 200 mg BID) administered in dogs, reversible hematology changes consistent with bone marrow toxicity became apparent at Day 7 with increasing severity from Day 14 onward. Dosing of MK-4482 up to 800 mg Q12H for 5.5 days has been generally well tolerated by healthy participants in a Phase 1 clinical study; on review of preliminary blinded safety data, no clinically meaningful trends have been observed for changes in clinical laboratory values, vital signs, or ECGs as a function of dose or treatment. Specifically, there have been no clinically significant abnormalities observed in the hematological laboratory tests. Overall, preclinical and Phase 1 clinical observations to date support a ~5-day dosing duration for MK-4482.

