### 8.1.8.1 Timing of Dose Administration

Study staff will administer the appropriate number of capsules of study intervention per the pharmacy manual Q12H ( $\pm 2$  hours) each day for 10 doses. Study intervention can be administered without regard to food. Refer to Section 8.6 for details regarding PK collection.

- For participants that begin dosing in the morning on Day 1, the EOT visit will occur on Day 5. PK specimens will be collected at the EOT visit in association with the 9th dose, and the final 10th dose will occur in the evening on Day 5.
- For participants that begin dosing in the evening on Day 1, the EOT visit will occur on Day 6. PK specimens will be collected at the EOT visit in association with the 10th dose on Day 6.

As outlined in the SoA, the first dose of study intervention is preferably administered on Day 1 but may be administered within 24 hours of randomization, therefore it is possible that dosing may not begin until Day 2.

- For participants that begin dosing in the morning on Day 2, the EOT visit will occur on Day 6. PK specimens will be collected at the EOT visit in association with the 9th dose, and the final 10th dose will occur in the evening on Day 6.
- For participants that begin dosing in the evening on Day 2, the EOT visit will occur on Day 7. PK specimens will be collected at the EOT visit in association with the 10th dose on Day 7.

If the EOT visit occurs on Day 6, no additional visit is required on Day 5. And if the EOT visit occurs on Day 7, no additional visits are required on Day 5 or Day 6.

The timing of the morning dose on the EOT visit will be observed by site staff/delegate and should be aligned with the timing of blood collection for PK analyses at EOT (SoA, Section 1.3). For participants who are discharged prior to EOT, if the participant takes their

EOT dose without observation by study staff, and prior to the pre-dose PK blood draw, then the timing of the dose will be reported from the Study Medication Diary to study staff by the participant or legally acceptable representative and recorded in the appropriate source documentation.

For all doses, the timing of dose administration will be recorded by study staff. If the participant has been discharged, doses will be recorded in the Study Medication Diary.

If a participant misses a dose of the study intervention, then the following guidance should be followed:

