### **8.11.3 Participants who Discontinue or Withdraw**

Participants who discontinue study intervention prior to completion of the treatment period should complete the activities for the EOT visit at the time of discontinuing study intervention. Blood samples for PK will not be collected for participants who discontinue study intervention prior to their 9th or 10th dose. The participant should then be encouraged to complete all the remaining subsequent study visits after EOT as outlined in the SoA (Section 1.3). In the event that an active condition requires ongoing monitoring (eg, abnormal laboratory results, AEs, or progression of COVID-19 signs/symptoms), unscheduled visit(s) may be performed prior to the next study visit on Day 10.

Participants who withdraw from the study prior to completion of the treatment period should complete the activities for the EOT visit at the time of withdrawal. Blood samples for PK will not be collected for participants who discontinue from study prior to their 9th or 10th dose of study intervention. Participants who withdraw from the study after completion of the treatment period should be encouraged to complete all applicable activities scheduled for the Day 29 visit at the time of withdrawal. This visit should be conducted at the clinic or as a home visit if possible. If circumstances do not support an in-person visit, a virtual visit may be used; in this case, laboratory or other in-person measures would not be collected. Return of participant diaries and reconciliation of any study intervention should be coordinated if

relevant. Any AEs that are present at the time of withdrawal should be followed in accordance with the safety requirements outlined in Section 8.4.

Survival status at Day 29 is required for all randomized participants and should still be reported for participants who withdraw from the study where permitted by local guidelines.

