## **Continuous Safety Measures**

For continuous measures such as changes from baseline in laboratory and vital signs parameters, summary statistics for baseline, on-treatment, and change from baseline values will be provided by treatment group in table format. In addition, summary statistics for the difference between treatment groups will also be provided.

Table 6 Analysis Strategy for Safety Parameters

Safety Tier	Safety Endpoint a	p-value	95% CI for Treatment Comparison	Descriptive Statistics		
Tier 1	ECIs	X	X	X		
Tier 2	Any AE		X	X		
	Any Serious AE		X	X		
	Any Drug-Related AE		X	X		
	Any Serious and Drug-Related AE		X	X		
	Discontinuation due to AE		X	X		
	Discontinuation due to Drug-Related AE		X	X		
	Specific AEs by SOCs and PT (incidence $\geq 4$ participants in at least one of the treatment groups)		X	X		
	PDLCs b (incidence $\geq 4$ participants in at least one of the treatment groups)		X	X		
Tier 3	Specific AEs by SOC and PT (incidence $< 4$ participants in each of the treatment groups)			X		
	PDLCs b (incidence $< 4$ participants in each of the treatment groups)			X		
	Change from Baseline Results (Labs, Vital Signs)			X		
Note: AE=adverse event; CI=confidence interval; PT=preferred term; SOC=system organ class; PDLC=pre-defined limit of change; X=results will be provided						
a Adverse Event references refer to both Clinical and Laboratory AEs. b Includes only those endpoints not pre-specified as Tier 1 or not already pre-specified as Tier-2 endpoints..						

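### The graded laboratory (PDLC) table takes in only 2 of the 5 scheduled post-baseline draws; and the Pulmonary+ diagnoses at Day 29 rest on an AE reporting period that the protocol describes in two ways

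*Combined protocol and SAP*

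**What the plan says.** **Laboratory window.** In Section 9.4.2, PDLC classification uses each participant's worst values "based on their most abnormal laboratory test values, in the direction of interest, while on study intervention", and for the laboratory summaries "participants must have both a baseline and post-randomization on-treatment measurement to be included". Section 9.6.2 uses the same term for continuous measures: "summary statistics for baseline, on-treatment, and change from baseline values will be provided by treatment group in table format". Neither section defines on-treatment. The Schedule of Activities (SoA, Section 1.3) gives "EOT=End of Treatment (day of last study intervention dose", and Section 8.1.8.1 places that day on Day 5, 6 or 7; at the late end, "For participants that begin dosing in the evening on Day 2, the EOT visit will occur on Day 7". The SoA central laboratory row has post-baseline draws at Day 3, EOT, Day 10, Day 15 and Day 29, with "Hematology and Chemistry at all indicated time points". A participant who stops early "should complete the activities for the EOT visit at the time of discontinuing study intervention" (Section 8.11.3).

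**Why hematology is watched.** Section 4.3.1 reports that in a 28-day dog study "reversible hematology changes consistent with bone marrow toxicity became apparent at Day 7 with increasing severity from Day 14 onward". Section 4.2.1.2 gives the preclinical findings as the reason for CBC and platelet monitoring.

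**Pulmonary+.** Section 9.4.1.1 says the score is derived by program from eCRF data and lists the sources. For the category 4 diagnoses in Section 10.8.1 (stroke, myocarditis, thrombosis and others), adverse events are the only source on that list. Section 8.4.1 requires all AEs to be reported until 14 days after treatment stops, and later only SAEs considered related. Table 3 requires all events through a Protocol-specified Follow-up Period that it does not define. The SoA schedules AE review at Day 29, but footnote h ties that review to Section 8.4.

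**The concern.** The PDLC table is the planned display that grades every measured laboratory value and compares the arms. If it stops at the last dose, a difference in neutrophil or hemoglobin grade that first appears afterwards is absent from the table and its listing, although the blood is drawn and tested. The ECIs in Section 8.4.7 cover only confirmed platelets <50,000/µL, confirmed amylase or lipase >3X ULN, and the liver pattern. Other results reach the AE tables only through the investigator's judgment, and Section 8.3.4 sets aside findings associated with the underlying disease unless they are more severe than expected.

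The second point has a different mechanism: an efficacy score may look for events after the period in which they must be reported. A participant with a new, unrelated category 4 diagnosis late in follow-up could then be scored in a better category at Day 29.

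**Working it through.** **Inputs.** Last dose L = Day 5, 6 or 7 for a full course (8.1.8.1). Draws at Day 3, EOT, Day 10 (±1), Day 15 (+3) and Day 29 (+3) (SoA). All-AE period ends at L + 14 (8.4.1).

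**The plan's own figures first.** Section 8.3.5 puts Day 29 about 24 days after the last dose: 29 − 5 = 24, 29 − 6 = 23, 29 − 7 = 22, which agrees. Table 11 confirms the draw count. Hematology and chemistry volumes appear at all five post-baseline visits, and the visit subtotals add up: 30.5 + 4.5 + 30.5 + 23 + 4.5 + 24 = 117 mL. Adding PK gives 117 + 15 = 132 (Part 1), 117 + 9 = 126 (Part 2) and 117 + 15 + 80 = 212 (PBMC cohort), all as stated.

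**Days after last dose, and end of the all-AE period**

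| Last dose L | Day 10 − L | Day 15 − L | Day 29 − L | L + 14 | 29 − (L + 14) |
|---|---|---|---|---|---|
| Day 5 | 5 | 10 | 24 | Day 19 | 10 |
| Day 6 | 4 | 9 | 23 | Day 20 | 9 |
| Day 7 | 3 | 8 | 22 | Day 21 | 8 |

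**Scheduled draws counted, full course.**
- As written: the Day 10 visit can be no earlier than Day 9, after the latest last dose (Day 7). Only Day 3 and EOT count: 2 of 5.
- Through 14 days after last dose: the latest Day 15 visit is Day 18, which is 13, 12 or 11 days after the last dose, so it is inside: 4 of 5.
- Through Day 29: 5 of 5.

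**Early stoppers.** A participant who stops on Day 1 or 2 has at most 1 scheduled draw counted, because the EOT activities move to the time of discontinuation. For L = 1, 2, 3, 4 the all-AE period ends on Day 15, 16, 17, 18, leaving 14, 13, 12, 11 days to Day 29. For L = 1 to 3, a Day 15 visit held on Day 18 falls 3, 2 or 1 days after that cut-off.

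**Pulmonary+.** For a full course, 8 to 10 days before nominal Day 29 lie outside the all-AE period of Section 8.4.1. If the visit is held on Day 32, the gap is 13, 12 or 11 days for L = 5, 6, 7. The documents give no rate for these events, so neither the number missed nor any bias can be estimated.

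**The case against.** A reader might infer that post-treatment laboratory data go uncompared altogether. The documents do not support that. Laboratory AEs enter the Tier 2 and Tier 3 tables (Table 6, footnote a), carry DAIDS grades (Section 10.3.4) and are reported to 14 days after treatment. Platelets, amylase/lipase and the liver pattern are Tier 1 ECIs with no on-treatment limit. Section 8.3.4 asks for repeat testing of clinically significant abnormalities seen within 14 days of the last dose, and the eDMC reviews accumulating safety data. Unscheduled samples taken during dosing also count toward the PDLC table. Table 6 lists change from baseline without a window, so later values are not shown to be excluded from the continuous summaries. What stands is that no planned display systematically grades and compares all post-treatment values.

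Section 9.5.2, which admits any value after at least one dose, might be read either as contradicting Section 9.4.2 or as curing it. It does neither: it sets a minimum for inclusion and does not say which values are classified.

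A reader might also infer that late marrow toxicity is expected. It is not. The dog changes arose under continued dosing and were reversible, dosing here ends by Day 7 for a full course, and Section 4.2.1.2 reports no clinically significant hematology abnormality in Phase 1. The Phase 1 lipase rises did not appear dose related, so they are no basis for this point.

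For Pulmonary+, the tempting reading is a proven data gap across category 4. The oxygen criterion of that category has its own data source. AEs that begin inside the period are followed to resolution (8.4.3). Hospitalizations are collected throughout (8.4.6), and re-hospitalization details are recorded (8.2.5), although neither is named as a scoring source. If Table 3's follow-up period means Day 29, the gap largely closes. This is therefore a conflict to reconcile, with a possible loss if Section 8.4.1 governs.

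**Conclusion.** Both points hold in limited form and are minor.

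(1) Taking the words of Section 9.4.2 as they stand, and counting the EOT draw as on treatment, the PDLC table uses 2 of 5 scheduled post-baseline draws for a full course. The three left out fall nominally 3-5, 8-10 and 22-24 days after the last dose. An on-treatment display is legitimate, but on its own it cannot show a later shift in neutrophil or hemoglobin grade.

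(2) If Section 8.4.1 governs, new unrelated category 4 diagnoses in the 8-10 days before Day 29 may be missed. That affects one of five time points of a secondary endpoint outside the alpha hierarchy. The documents also do not say whether such an event must be ongoing at the assessment to count.

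Neither point changes the primary result, type I error or sample size.

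**What to change.** **Laboratory displays.** In Sections 9.4.2 and 9.6.2, state which draws count as on-treatment, including the EOT draw of a participant who stops early. Keep that display. Add PDLC and change-from-baseline displays from first dose through 14 days after last dose, and from first dose through Day 29. The data are already collected, so the cost is wording and programming. Section 9 lets non-confirmatory changes made before unblinding go into the sSAP. The downside is that longer windows admit more disease-related abnormalities, possibly unequally by arm, which is why the on-treatment display should stay alongside.

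**Pulmonary+.** Reconcile Section 8.4.1 with Table 3, and with the remark in Section 9.4.2 about SAEs throughout the study. Record the category 4 diagnoses at the existing Day 29 visit regardless of causality or seriousness, and/or name the re-hospitalization data as a scoring source in Section 9.4.1.1. State whether an event must be ongoing to count. This needs no new visit or blood draw, only a short eCRF entry, but changing the reporting text may require a protocol amendment with regulatory and IRB/IEC review.

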### **9.5 Analysis Populations**

#### **9.5.1 Efficacy Analysis Populations**

The MITT population will serve as the primary population for the analysis of efficacy data for both parts of this study. The MITT population consists of all randomized participants who received at least 1 dose of study intervention. Part 1 (Phase 2) and Part 2 (Phase 3) of the study will be analyzed separately for efficacy endpoints. Therefore, the MITT population for Part 2 will not include Part 1 participants, and vice versa.

A supportive analysis using the Per-Protocol population will be performed for primary and secondary efficacy endpoint(s) for Part 2. The Per-Protocol population excludes participants due to deviations from the protocol that may substantially affect the results of the primary efficacy endpoint.

The final determination on protocol deviations, and thereby the composition of the Per-Protocol population, will be made prior to the final unblinding of the database and will be documented in a separate memo.

Participants will be included in the treatment group to which they are randomized for the analysis of efficacy data using both the MITT and Per-Protocol populations.

### **9.5.2 Safety Analysis Populations**

Safety Analyses will be conducted in the APaT population, which consists of all randomized participants who received at least one dose of study treatment. Participants will be included in the treatment group corresponding to the study treatment they actually received for the analysis of safety data using the APaT population. This will be the treatment group to which they are randomized except for participants who take incorrect study treatment for the entire treatment period; such participants will be included in the treatment group corresponding to the study treatment actually received. Part 1 (Phase 2) and Part 2 (Phase 3) of the study will be combined for the final analysis of safety endpoints. The data presentations will focus on the selected dose group for MK-4482 and placebo.

At least one laboratory value or vital sign obtained subsequent to at least one dose of study treatment is required for inclusion in the analysis of the respective safety parameter. To assess change from baseline, a baseline measurement is also required.

